Related adverse events include possibly, probably, and definitely responses to relationship to study drug question.

Table 14.3.1.1.5: Summary of Severe Treatment-Emergent Adverse Events by MedDRA System Organ Class and Preferred Term (Safety Population)

Table 14.3.1.1.6: Summary of Treatment-Emergent Adverse Events Leading to Study Discontinuation by MedDRA System Organ Class and Preferred Term (Safety Population)

Table 14.3.1.1.7: Summary of Treatment-Emergent Abuse-Related Adverse Events by MedDRA System Organ Class and Preferred Term (Safety Population)

Table 14.3.1.2.1.1: Summary of Chemistry Results by Visit
(Safety Population)
(Page 1 of y)

Test Name (Units)	Vehicle QD (N=xx)	Vehicle BID (N=xx)	Vehicle Combined (N=xx)	BTX 1503 5% BID (N=xx)	BTX 1503 5% QD (N=xx)	BTX 1503 2.5% QD (N=xx)	BTX 1503 Combined (N=xx)
Baseline							
n	xx	xx	xx	xx	xx	xx	xx
Mean	xx.x	xx.x	xx.x	xx.x	xx.x	xx.x	xx.x
SD	xx.xx	xx.xx	xx.xx	xx.xx	xx.xx	xx.xx	xx.xx
Median	xx.x	xx.x	xx.x	xx.x	xx.x	xx.x	xx.x
Min., Max.	xx, xx	xx, xx	xx, xx	xx, xx	xx, xx	xx, xx	xx, xx
Day 84							
n	xx	xx	xx	xx	xx	xx	xx
Mean	xx.x	xx.x	xx.x	xx.x	xx.x	xx.x	xx.x
SD	xx.xx	xx.xx	xx.xx	xx.xx	xx.xx	xx.xx	xx.xx
Median	xx.x	xx.x	xx.x	xx.x	xx.x	xx.x	xx.x
Min., Max.	xx, xx	xx, xx	xx, xx	xx, xx	xx, xx	xx, xx	xx, xx
Change from Baseline							
n	xx	xx	xx	xx	xx	xx	xx
Mean	xx.x	xx.x	xx.x	xx.x	xx.x	xx.x	xx.x
SD	xx.xx	xx.xx	xx.xx	xx.xx	xx.xx	xx.xx	xx.xx
Median	xx.x	xx.x	xx.x	xx.x	xx.x	xx.x	xx.x
Min., Max.	xx, xx	xx, xx	xx, xx	xx, xx	xx, xx	xx, xx	xx, xx

[repeat for each test]

SOURCE: USERNAME\SPONSOR\PROJECT\JOBNAME (DATE,TIME)

Programming note: Chemistry tests include: Glucose, Albumin, Total Protein, Calcium, Sodium, Potassium, Chloride, CO₂ (bicarbonate), BUN, Creatinine, Alkaline Phosphatase, ALT, AST, and Total Bilirubin. Test names will be standardized to CDISC Controlled Terminology.

Table 14.3.1.2.1.2: Shift Table for Chemistry Results
(Safety Population)
(Page 1 of y)

Test Name (Units)		Baseline (N=xx)		
		BNL	WNL	ANL
Vehicle QD (N=xx)	Day 84 (N^a=xx)			
	BNL	xx (xx.x%)	xx (xx.x%)	xx (xx.x%)
	WNL	xx (xx.x%)	xx (xx.x%)	xx (xx.x%)
	ANL	xx (xx.x%)	xx (xx.x%)	xx (xx.x%)
Vehicle BID (N=xx)	Day 84 (N^a=xx)			
	BNL	xx (xx.x%)	xx (xx.x%)	xx (xx.x%)
	WNL	xx (xx.x%)	xx (xx.x%)	xx (xx.x%)
	ANL	xx (xx.x%)	xx (xx.x%)	xx (xx.x%)
Vehicle Combined (N=xx)	Day 84 (N^a=xx)			
	BNL	xx (xx.x%)	xx (xx.x%)	xx (xx.x%)
	WNL	xx (xx.x%)	xx (xx.x%)	xx (xx.x%)
	ANL	xx (xx.x%)	xx (xx.x%)	xx (xx.x%)

^a Number of subjects with both Baseline and Day 84 results for the given treatment group.

Note: BNL=Below Normal Limit, WNL=Within Normal Limit, ANL=Above Normal Limit.

Percentages are based on the number of subjects in the Safety population with both Baseline and Day 84 results.

SOURCE: USERNAME\SPONSOR\PROJECT\JOBNAME (DATE,TIME)

Table 14.3.1.2.1.2: Shift Table for Chemistry Results
(Safety Population)
(Page 2 of y)

Test Name (Units)		Baseline		
		BNL	WNL	ANL
BTX 1503 5% BID (N=xx)	Day 84 (N^a=xx)			
	BNL	xx (xx.x%)	xx (xx.x%)	xx (xx.x%)
	WNL	xx (xx.x%)	xx (xx.x%)	xx (xx.x%)
	ANL	xx (xx.x%)	xx (xx.x%)	xx (xx.x%)
BTX 1503 5% QD (N=xx)	Day 84 (N^a=xx)			
	BNL	xx (xx.x%)	xx (xx.x%)	xx (xx.x%)
	WNL	xx (xx.x%)	xx (xx.x%)	xx (xx.x%)
	ANL	xx (xx.x%)	xx (xx.x%)	xx (xx.x%)
BTX 1503 2.5% QD (N=xx)	Day 84 (N^a=xx)			
	BNL	xx (xx.x%)	xx (xx.x%)	xx (xx.x%)
	WNL	xx (xx.x%)	xx (xx.x%)	xx (xx.x%)
	ANL	xx (xx.x%)	xx (xx.x%)	xx (xx.x%)
BTX 1503 Combined (N=xx)	Day 84 (N^a=xx)			
	BNL	xx (xx.x%)	xx (xx.x%)	xx (xx.x%)
	WNL	xx (xx.x%)	xx (xx.x%)	xx (xx.x%)
	ANL	xx (xx.x%)	xx (xx.x%)	xx (xx.x%)

[Repeat for all tests]

^a Number of subjects with both Baseline and Day 84 results for the given treatment group.

Note: BNL=Below Normal Limit, WNL=Within Normal Limit, ANL=Above Normal Limit.

Percentages are based on the number of subjects in the Safety population with both Baseline and Day 84 results.

SOURCE: USERNAME\SPONSOR\PROJECT\JOBNAME (DATE,TIME)

Repeat Table 14.3.1.2.1.1 for the following:

Table 14.3.1.2.2.1: Summary of CBC Results by Visit (Safety Population)

Programming note: CBC tests include: WBC (with differentials for ANC, Lymphocytes, monocytes, eosinophils, and basophils), RBC, Hemaglobin, Hematocrit, MCV, MCH, MCHC, and Platelet Count. Test names will be standardized to CDISC Controlled Terminology.

Repeat Table 14.3.1.2.1.2 for the following:

Table 14.3.1.2.2.2: Shift Table for CBC Results (Safety Population)

Repeat Table 14.3.1.2.1.1 for the following:

Table 14.3.1.2.3.1: Summary of Numeric Urinalysis Results by Visit (Safety Population)

Repeat Table 14.3.1.2.1.2 for the following:

Table 14.3.1.2.3.2: Shift Table for Numeric Urinalysis Results (Safety Population)

Table 14.3.1.2.3.3: Summary of Character Urinalysis Results by Visit
(Safety Population)
(Page 1 of y)

Test Name (Units)	Vehicle QD (N=xx)	Vehicle BID (N=xx)	Vehicle Combined (N=xx)	BTX 1503 5% BID (N=xx)	BTX 1503 5% QD (N=xx)	BTX 1503 2.5% QD (N=xx)	BTX 1503 Combined (N=xx)
Baseline							
n	xx	xx	xx	xx	xx	xx	xx
xxxxxxx	xx (xx.x%)	xx (xx.x%)	xx (xx.x%)	xx (xx.x%)	xx (xx.x%)	xx (xx.x%)	xx (xx.x%)
xxxxxxx	xx (xx.x%)	xx (xx.x%)	xx (xx.x%)	xx (xx.x%)	xx (xx.x%)	xx (xx.x%)	xx (xx.x%)
xxxxxxx	xx (xx.x%)	xx (xx.x%)	xx (xx.x%)	xx (xx.x%)	xx (xx.x%)	xx (xx.x%)	xx (xx.x%)
Day 84							
n	xx	xx	xx	xx	xx	xx	xx
xxxxxxx	xx (xx.x%)	xx (xx.x%)	xx (xx.x%)	xx (xx.x%)	xx (xx.x%)	xx (xx.x%)	xx (xx.x%)
xxxxxxx	xx (xx.x%)	xx (xx.x%)	xx (xx.x%)	xx (xx.x%)	xx (xx.x%)	xx (xx.x%)	xx (xx.x%)
xxxxxxx	xx (xx.x%)	xx (xx.x%)	xx (xx.x%)	xx (xx.x%)	xx (xx.x%)	xx (xx.x%)	xx (xx.x%)

[repeat for each test]

Note: Percentages are based on the number of subjects in the Safety population with a non-missing result for the given test and visit.

SOURCE: USERNAME\SPONSOR\PROJECT\JOBNAME (DATE,TIME)

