6. STATISTICAL AND ANALYTICAL PLANS

6.1 General Methodology

All statistical processing will be performed using SAS® 9.3 or higher. No interim analyses are planned. This Phase 2 study is designed to identify the response to two different dosing frequencies and two concentrations of BTX 1503. Statistical tests applied to the outcomes will be exploratory. No adjustments for Type I error will occur.

Descriptive statistics will be used to provide an overview of the efficacy and safety results. For categorical parameters, the number and percentage of subjects in each category will be presented. For continuous parameters, descriptive statistics will include n (number of subjects), mean, standard deviation (SD), median, minimum and maximum.

The primary method of handling missing efficacy data in the ITT analysis set will be based on last observation carried forward (LOCF). Repeated measures analyses will be used on the observed data as a sensitivity analysis on the primary endpoint and the first secondary endpoint.

The efficacy analysis performed on the ITT population is considered the primary analysis. The efficacy analysis performed on the per-protocol (PP) population is considered supportive analysis.

The number of subjects in each analysis set will be summarized. Reasons for study withdrawal during the study will be summarized using frequencies and percentages by treatment group.

Reported AEs, medical history terms, and prior and concomitant procedures and therapies will be classified on the basis of Medical Dictionary for Regulatory Activities (MedDRA) terminology. Prior and concomitant medications will be classified on the basis of World Health Organization Drug Dictionary (WHO-DDE) terminology.

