6.1.5 Handling of Dropouts or Missing Data

All efforts will be made to minimize the occurrence of missing data. It is not expected that dropout rates will differ between groups. Therefore, the primary method of handling missing efficacy data in the ITT analysis set will be based on last observation carried forward (LOCF). Summary of efficacy and pharmacology variables for the PP subjects will be based on available data. No imputation will be done for non-efficacy related variables.

If a partial date is reported where the day is missing, then the day will be imputed as the first day of the month unless the month is the same month as the first application of study drug then the day will be that of first application with the month and year remaining the same. If a partial date is reported where the month is missing, then the month will be imputed to January unless the year is the same year as the first application of study drug then the month will be that of first application with the year remaining the same. If a partial date where both the day and month is missing, follow details as stated previously.

Missing AE start dates will be imputed using partial date imputation rules as previously described in this Section.

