6.8.1 Primary Efficacy Analysis

Absolute change from Baseline to Day 84 in inflammatory lesion counts will be analyzed using either parametric or non-parametric methods consistent with the statistical assumptions required to support the analyses. Specifically, the tests of superiority will be based on an ANCOVA with factors of treatment (with the vehicle treatment groups combined) and the respective Baseline lesion count as a covariate, or on ranked data submitted to an ANCOVA with factors of treatment and the respective Baseline lesion count as a covariate.

A skewness test, based on the methods presented by J.H. Zar (1984), will be applied to the residuals resulting from an ANCOVA. A two-sided p-value for the skewness test significant at 0.01 will imply the use of the non-parametric method. If a parametric analysis is indicated, the results of the parametric analysis will be considered the primary analysis. Should a non-parametric analysis be indicated, the absolute changes in inflammatory lesions will be rank transformed prior to submitting them to the ANCOVA. Results of the rank-transformed analyses then will be considered the primary analysis; however, results of the non-ranked transformed analyses will also be presented.

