6.8.2 Secondary Efficacy Analysis

6.8.2.1 Lesion Counts

The absolute change from Baseline in non-inflammatory lesion count at Day 84 will be summarized similarly as absolute change from Baseline for inflammatory lesion count (primary efficacy endpoint). Percent change from Baseline to Day 84 in inflammatory and non-inflammatory lesion counts will be analyzed using the same ANCOVA method described for the primary endpoint.

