6.9 Sensitivity Analyses

A sensitivity analysis will be performed using the ITT population. The primary and the first secondary endpoints (change from Baseline in inflammatory and non-inflammatory lesion counts) will be analyzed using a repeated measures ANCOVA, with treatment group and visit as independent factors and the Baseline value as a covariate.

```
proc mixed data = datain method = ML;
  class SUBJECT TRT VISIT;
  model CHG = TRT VISIT TRT * VISIT BASE / solution;
  repeated VISIT / subject = SUBJECT type = cs;
  lsmeans TRT | VISIT / diff;
run;
```

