Table 14.2.2.1.3: Sensitivity Analysis of Secondary Efficacy Endpoint: Summary of Absolute Change from Baseline in Non-Inflammatory Lesion Count at Day 84 (ITT Population)

Repeated Measures Analysis on Observed Data	Vehicle QD (N=xx)	Vehicle BID (N=xx)	Vehicle Combined (N=xx)	BTX 1503 5% BID (N=xx)	BTX 1503 5% QD (N=xx)	BTX 1503 2.5% QD (N=xx)
Change from Baseline in Non-Inflammatory Lesion Counts						
n	xx	xx	xx	xx	xx	xx
Mean	xx.x	xx.x	xx.x	xx.x	xx.x	xx.x
SD	xx.xx	xx.xx	xx.xx	xx.xx	xx.xx	xx.xx
Median	xx.x	xx.x	xx.x	xx.x	xx.x	xx.x
Min., Max.	xx, xx	xx, xx	xx, xx	xx, xx	xx, xx	xx, xx
LSMean ^a			xx.x	xx.x	xx.x	xx.x
LSSD ^a			xx.xx	xx.xx	xx.xx	xx.xx
P-value vs. Combined Vehicle ^a				0.xxxx	0.xxxx	0.xxxx

^a Least squares mean, standard deviation, and contrast p-values from a repeated measures analysis of covariance with factors of treatment group (vehicle treatment groups included as single combined treatment group), visit, treatment by visit interaction, and corresponding baseline lesion count as the covariate. Note: No imputations were made for missing data.

SOURCE: USERNAME\SPONSOR\PROJECT\JOBNAME (DATE,TIME)

Table 14.2.2.1.4: Subgroup Summary of Secondary Efficacy Endpoint: Absolute Change from Baseline in Non-Inflammatory Lesion Count at Day 84
(PP Population)
(Page 1 of 16)

Baseline Inflammatory Lesion Count < median (xx)						
	Vehicle QD	Vehicle BID	Vehicle Combined	BTX 1503 5% BID	BTX 1503 5% QD	BTX 1503 2.5% QD
	(N=xx)	(N=xx)	(N=xx)	(N=xx)	(N=xx)	(N=xx)
Change from Baseline in Non-Inflammatory Lesion Counts						
n	xx	xx	xx	xx	xx	xx
Mean	xx.x	xx.x	xx.x	xx.x	xx.x	xx.x
SD	xx.xx	xx.xx	xx.xx	xx.xx	xx.xx	xx.xx
Median	xx.x	xx.x	xx.x	xx.x	xx.x	xx.x
Min., Max.	xx, xx	xx, xx	xx, xx	xx, xx	xx, xx	xx, xx
Baseline Inflammatory Lesion Count ≥ median (xx)						
	Vehicle QD	Vehicle BID	Vehicle Combined	BTX 1503 5% BID	BTX 1503 5% QD	BTX 1503 2.5% QD
	(N=xx)	(N=xx)	(N=xx)	(N=xx)	(N=xx)	(N=xx)
Change from Baseline in Non-Inflammatory Lesion Counts						
n	xx	xx	xx	xx	xx	xx
Mean	xx.x	xx.x	xx.x	xx.x	xx.x	xx.x
SD	xx.xx	xx.xx	xx.xx	xx.xx	xx.xx	xx.xx
Median	xx.x	xx.x	xx.x	xx.x	xx.x	xx.x
Min., Max.	xx, xx	xx, xx	xx, xx	xx, xx	xx, xx	xx, xx

Note: No imputations were made for missing data.

SOURCE: USERNAME\SPONSOR\PROJECT\JOBNAME (DATE,TIME)

Table 14.2.2.1.4: Subgroup Summary of Secondary Efficacy Endpoint: Absolute Change from Baseline in Non-Inflammatory Lesion Count at Day 84
(PP Population)
(Page 2 of 16)

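### The repeated-measures sensitivity model fits one Baseline slope for all four visits, so its Day 84 estimate can differ slightly from the ANCOVA it checks even when no data are missing

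*SAP*

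**What the plan says.** SAP 6.9 gives the code for the sensitivity analysis. The fixed effects are "model CHG = TRT VISIT TRT * VISIT BASE / solution", the covariance is "repeated VISIT / subject = SUBJECT type = cs", and the call is "proc mixed data = datain method = ML". Treatment effects may vary by visit, but the Baseline effect may not. Footnote a of the sensitivity version of Table 14.2.1.3 (inflammatory count, the primary endpoint) and of Table 14.2.2.1.3 (non-inflammatory count) lists the same terms: treatment with the vehicle groups combined, "visit, treatment by visit interaction, and corresponding baseline lesion count as the covariate".

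The analysis being checked is in SAP 6.8.1: an "ANCOVA with factors of treatment (with the vehicle treatment groups combined) and the respective Baseline lesion count as a covariate", run on change at Day 84 only. SAP 6.8.2.1 says that absolute change in non-inflammatory count "will be summarized similarly as absolute change from Baseline for inflammatory lesion count".

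SAP 6.1 states the purpose: "Repeated measures analyses will be used on the observed data as a sensitivity analysis on the primary endpoint and the first secondary endpoint". SAP 6.1.5 makes LOCF the main method for missing efficacy data. No other sensitivity analysis is planned.

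**The concern.** A sensitivity analysis of missing-data handling is easiest to read when it differs from the main analysis only in that handling. Here the Baseline adjustment differs as well. The outcome is absolute change, and Protocol 5.1 admits 20 to 50 inflammatory and 20 to 100 non-inflammatory lesions. If counts fall roughly in proportion to Baseline, the slope of change on Baseline steepens as the fall grows. The ANCOVA then adjusts Day 84 with the Day 84 slope, while the repeated-measures model adjusts it with a slope averaged over the four visits. A reader who compares the two tables could put down to LOCF a difference that would be there with nobody missing.

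**Working it through.** **Inputs from the documents.** The model terms, covariance and estimation method are quoted above. There are 90 subjects per active arm and 45 + 45 = 90 on combined vehicle (SAP 7); 3 × 90 + 2 × 45 = 360. Baseline ranges are from Protocol 5.1. The plan states no slope, residual SD, effect size or dropout rate, so it has no figure to reproduce.

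**Step 1: algebra for complete data.** Let dY be the raw Day 84 difference between arms, dX the Baseline difference, b84 the Day 84 slope and bm the mean of the four visit slopes. Under compound symmetry with complete data, the common slope equals bm.
- ANCOVA estimate = dY − b84 × dX
- SAP 6.9 estimate = dY − bm × dX
- Gap (SAP 6.9 minus ANCOVA) = (b84 − bm) × dX

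With BASE*VISIT added, every term is crossed with visit and the Day 84 estimate becomes dY − b84 × dX, the same as the ANCOVA.

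**Step 2: check by fitting.** One complete dataset was simulated with four groups of 90, strong slope drift and rising residual SD. dX was −0.669.

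| Model | Day 84 estimate | SE |
|---|---|---|
| ANCOVA at Day 84 | −2.8164 | 1.673 |
| SAP 6.9 as coded | −2.6288 | 1.413 |
| SAP 6.9 plus BASE*VISIT | −2.8164 | 1.390 |

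The gap is −2.6288 + 2.8164 = 0.1876. Dividing by −0.669 gives b84 − bm = −0.28, close to the −0.30 built into the data. The added term removes the gap in the estimate but not in the SE. A second four-group complete dataset behaved the same way: −5.63 for the ANCOVA against −5.35 as coded, with an exact match once the term was added.

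**Step 3: size under assumptions.** Baseline is taken as uniform over the eligible range.
- SD of Baseline: 30/√12 = 8.66 (inflammatory) and 80/√12 = 23.09 (non-inflammatory).
- SD of dX: multiply by √(2/90) = 0.149, giving 1.29 and 3.44.
- Moderate drift, slopes −0.2, −0.3, −0.4, −0.5: b84 − bm = −0.5 + 0.35 = −0.15.
- Strong drift, slopes −0.1, −0.3, −0.5, −0.7: b84 − bm = −0.7 + 0.4 = −0.30.
- Mean absolute gap ≈ 0.798 × |b84 − bm| × SD of dX: 0.15 and 0.31 lesion (inflammatory), 0.41 and 0.82 (non-inflammatory).

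Simulation used 2000 complete trials per scenario and residual correlation 0.75 to the power of the visit lag. Residual SD was flat at 10 or rose from 7 to 11.5, doubled for non-inflammatory counts.

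| | Equal slopes (−0.3) | Moderate drift | Strong drift |
|---|---|---|---|
| Inflammatory: mean absolute gap | 0.03 | 0.16 | 0.31 |
| Inflammatory: 95th percentile | 0.10–0.12 | 0.40 | 0.77–0.78 |
| Non-inflammatory: mean absolute gap | 0.06–0.07 | 0.40–0.41 | 0.80–0.81 |
| Non-inflammatory: 95th percentile | 0.21–0.22 | 1.03 | 1.96–2.01 |
| Mean absolute gap as share of ANCOVA SE | about 2% | 9–14% | 18–27% |
| True SE relative to ANCOVA | 1.00 | 1.01–1.02 | 1.02–1.06 |

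The ANCOVA SE was about 1.5 to 1.7 (inflammatory) and 3.0 to 3.4 (non-inflammatory). The signed gap averaged about zero in every scenario.

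**Step 4: precision by formula.** The true variance ratio is about 1 + (b84 − bm)² × SD_base² / SD_resid². For non-inflammatory counts with strong drift and residual SD 20, it is 1 + 0.09 × 533/400 = 1.12, an SE ratio of 1.06, as simulated.

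**The case against.** A common Baseline slope is a legitimate prespecified simplification. It does not conflict with SAP 6.1.4, and no passage requires the sensitivity model to reproduce the ANCOVA on complete data. Protocol 9.4.9 makes MMRM optional, all tests are exploratory without Type I adjustment (SAP 6.1.8), and no decision rule depends on this table. The sizes rest on assumed slopes and SDs. All of this stands, and it keeps the point minor. It does not remove the point, because this is the only planned check on LOCF and the mismatch is avoidable.

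Three stronger readings are tempting, and the documents do not support them.
- *The model is biased.* On complete data the gap averages zero under randomisation. Bias needs slope drift together with dropout that depends on Baseline differently by arm. A deliberate stress case had about 19% missing at Day 84, dropout log-odds of +1 and −1 per Baseline SD in the two arms, and slopes −0.10, −0.20, −0.35, −0.45. It gave a bias of 1.4 non-inflammatory or 0.6 inflammatory lesions, which BASE*VISIT removed. With equal slopes there was none. The documents give no reason to expect such dropout, and SAP 6.1.5 expects similar rates across groups.
- *The model loses precision.* The loss is nil with stable slopes and at most about 6% of the SE in the scenarios run. It need not show in the output: with rising variance the coded model reports a smaller SE than the ANCOVA (1.39 to 1.42 against 1.71 to 1.72 for inflammatory counts).
- *After the change, any remaining gap is due to missing data.* That holds only for the point estimate relative to its complete-data benchmark. Compound symmetry with ML pools variance over visits. With rising variance, null rejection at a nominal two-sided 5% was about 11% as coded and stayed at 10 to 11% with BASE*VISIT. Once data are missing, the covariance choice also affects the estimate.

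**Conclusion.** The concern holds as a minor specification point, equally for the primary endpoint and the non-inflammatory secondary. The single slope follows directly from the SAP 6.9 code and both footnotes, and the complete-data gap formula is exact under the coded covariance. Its practical size is not known from the documents: about 0.02 SE if the Baseline slope is stable over visits, and roughly 0.1 to 0.3 SE under the assumed moderate to strong drift. It averages zero on complete data and comes with a true SE 0 to 6% larger. It is unlikely to change a conclusion, but it makes the comparison with LOCF less clean than it could be.

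**What to change.** In SAP 6.9, change the model statement to `model CHG = TRT VISIT TRT*VISIT BASE BASE*VISIT / solution;` and report the treatment LS means and contrasts at Day 84. Add the Baseline-by-visit interaction to footnote a of Table 14.2.2.1.3 and of the sensitivity Table 14.2.1.3 (that number is also used for a subgroup table, so name the sensitivity one). Compare the result with the unranked ANCOVA, which SAP 6.8.1 presents even when the skewness rule makes the ranked analysis primary.

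The cost is three degrees of freedom at n = 360 and two footnote edits. No new covariate is introduced, so SAP 6.1.4 is unaffected. The change aligns the complete-data point estimate only. Making SEs and p-values comparable is a separate decision about the compound-symmetry structure and ML estimation.

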7.2. Laboratory Procedures/Evaluations

7.2.1. Clinical Laboratory Evaluations

For all subjects, a CBC, chemistry, and urinalysis will be conducted at the Baseline and Day 84 Visits. Details are provided in the Laboratory Manual. Blood samples will be taken per standard venipuncture techniques. The following will be assessed:

CBC: White blood cell (WBC) count (with automated differential for absolute neutrophils, lymphocytes, monocytes, eosinophils, and basophils), red blood cell (RBC) count, haemoglobin, hematocrit, mean corpuscular volume (MCV), mean corpuscular haemoglobin (MCH), mean corpuscular haemoglobin concentration (MCHC), and platelet count;

Chemistry: Glucose, albumin, total protein, calcium, sodium, potassium, chloride, CO₂ (bicarbonate), blood urea nitrogen (BUN), creatinine, alkaline phosphatase, alanine amino transferase (ALT), aspartate amine transferase (AST), and total bilirubin;

Urinalysis: Color, clarity, specific gravity, pH, protein, glucose, and leukocyte esterase. If the results are abnormal or further analysis is requested by the site, the sample will undergo microscopic analysis for red blood cells, white blood cells, and squamous epithelial cells.

For all WOCBP, a UPT will be conducted at the Screening Visit, Baseline Visit (if > 7 days from Screening Visit), and the Day 28, Day 56, and Day 84 Visits. Details for collecting and testing urine for the UPT are provided in the Laboratory Manual.

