9.4.2. Safety Analyses

All subjects who receive at least one confirmed dose of study drug and have at least one post-Baseline assessment will be included in the safety analyses.

All treatment-emergent adverse events (TEAEs) reported during the study will be recorded and classified based on MedDRA terminology. Treatment-emergent adverse events are those AEs with an onset on or after the first application of study medication. All reported TEAEs will be summarized by treatment group, the number of subjects reporting events, system organ class, preferred term, severity, relationship to study drug, and seriousness. When summarizing events by causality and severity, each subject will be counted only once within a system organ class or a preferred term by using the event with the greatest relationship and highest severity within each classification.

Serious adverse events (SAEs) will be summarized by cohort, system organ class, preferred term, severity, outcome and relationship to study drug; and all SAEs will be listed by subject. In addition, a list of subjects who prematurely discontinue from the study due to an AE and the reason for discontinuation will be provided.

Concomitant medication will be mapped to ATC Level 2 using the WHODrug dictionary. The number and percentage of subjects reporting each medication will be summarized. Medications taken by each subject will be listed.

Changes from Baseline in safety laboratory assessments (CBC, chemistry and urinalysis) at Day 84 will be summarized using shift tables. Abnormal values will be summarized. Laboratory values will be listed by subject.

Cutaneous tolerability will be assessed at the Baseline, Day 14, Day 28, Day 56 and Day 84 Visits. Summaries will present frequencies and percentages for the grading of each of the signs/symptoms that was performed at each scheduled visit/time point combination. The summary of cutaneous tolerability assessment scores table will present summary statistics for the scores ('None'=0, 'Slight'=1, 'Moderate'=2 and 'Severe'=3) and the change from Baseline values at each scheduled post-Baseline visits/time point for each of the signs/symptoms. Listings will be provided by subject.

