6.10.3 Clinical Laboratory Evaluation

Laboratory test results will be summarized with descriptive statistics at Baseline and Day 84. Additionally, shifts from Baseline to Day 84 in laboratory test results based on normal ranges will be summarized with frequency counts and percentages. Individual laboratory test results as well as pregnancy test results will be presented in a by-subject listing.

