8. CHANGES IN THE PLANNED ANALYSES

There are no changes in the conduct of the study or planned analyses.

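### The SAP plans a urinalysis shift table for numeric results only, so new abnormalities in character-valued items generally cannot be counted by arm from any planned laboratory summary table

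*SAP*

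**What the plan says.** **Protocol.** Section 9.4.2 states: "Changes from Baseline in safety laboratory assessments (CBC, chemistry and urinalysis) at Day 84 will be summarized using shift tables". It goes on: "Abnormal values will be summarized. Laboratory values will be listed by subject". So there are three separate undertakings (shift tables, a summary of abnormal values, and listings), and urinalysis is named in the first. Section 7.2.1 gives the routine panel as "Urinalysis: Color, clarity, specific gravity, pH, protein, glucose, and leukocyte esterase", with microscopy only if the result is abnormal or the site asks for it. Urinalysis is scheduled at Baseline and Day 84 only.

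**SAP text.** Section 6.10.3 says that "shifts from Baseline to Day 84 in laboratory test results based on normal ranges will be summarized with frequency counts and percentages", and separately that "Individual laboratory test results as well as pregnancy test results will be presented in a by-subject listing". Section 8 says: "There are no changes in the conduct of the study or planned analyses".

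**SAP shells.** Urinalysis has three tables: a by-visit summary of numeric results, a shift table ("Table 14.3.1.2.3.2: Shift Table for Numeric Urinalysis Results (Safety Population"), and "Table 14.3.1.2.3.3: Summary of Character Urinalysis Results by Visit". The shift table reuses the chemistry layout, which crosses below, within and above normal limits at Baseline with the same classes at Day 84, among subjects who have both results. The character table shows categories at Baseline and, in a separate block, at Day 84. Its percentages are taken over non-missing results for that test at that visit.

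**The concern.** The protocol's shift-table commitment covers urinalysis without exception, but the shells meet it only for numeric results. The character table does not pair a subject's two results, does not code them normal or abnormal, and shows no change. No other laboratory table in the index summarizes abnormal character results. The analysis is therefore narrower than the protocol states, and the section of the SAP meant for such changes reports none.

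Baseline against Day 84 is the only planned on-treatment urinalysis comparison in the trial. For any item reported as a category, the clinical study report could show how many subjects fell in each category at each visit. In general it could not show how many in each arm went from normal to abnormal on treatment.

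**Working it through.** The plan gives no figure to reproduce. The check is a comparison of commitments with shells, followed by a small illustration.

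**1. Commitment against delivery**

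- Shift table for urinalysis (protocol 9.4.2): delivered for numeric results in Table 14.3.1.2.3.2, not delivered for character results.
- Summary of abnormal values (protocol 9.4.2): for character results, Table 14.3.1.2.3.3 counts categories but does not classify them as normal or abnormal.
- Listing by subject (protocol 9.4.2, SAP 6.10.3): delivered in Listing 16.2.8.2.1.3. It repeats the CBC listing layout, with results by visit, reference range, indicator and investigator clinical-significance flag.

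**2. How many items are affected**

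Protocol 7.2.1 lists seven routine items. Neither document assigns them to the numeric or the character tables.

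- Color and clarity are descriptive: 2 items.
- Protein, glucose and leukocyte esterase may be reported in grades (assumption): 0 to 3 more items.
- Range: 2 + 0 = 2 to 2 + 3 = 5 of 7.

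The result type of the reflex microscopy items is also unstated, so they are left out of the count.

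**3. What two per-visit counts can show**

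Among N subjects with both results, let A0 be the number abnormal at Baseline and A84 the number abnormal at Day 84. Without the cross-classification, the number newly abnormal lies between

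max(0, A84 − A0) and min(A84, N − A0).

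The documents give no abnormality counts and no missing-data rate, so the counts here are assumed. Take an active arm of 90 (SAP section 7) in which 76 have a Day 84 sample. That leaves 14 without one, and 14/90 = 15.6%. Suppose 6 are protein-positive at each visit, and all 6 Baseline positives are among the 76.

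- Table 14.3.1.2.3.3 would show 6/90 = 6.7% at Baseline and 6/76 = 7.9% at Day 84. The percentage rises although the count does not, because the denominators differ.
- New positives: from max(0, 6 − 6) = 0 to min(6, 76 − 6) = 6. As a share of the 76 paired subjects this is 0% to 6/76 = 7.9%.

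Other assumed counts, with complete pairs in an arm of 90:

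| Abnormal at Baseline | Abnormal at Day 84 | New abnormalities |
|---|---|---|
| 5 | 5 | 0 to 5 |
| 8 | 8 | 0 to 8 |
| 5 | 10 | 5 to 10 |
| 0 | 5 | exactly 5 |

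The same ranges hold in a vehicle arm of 45. The last row is the exception: if nobody is abnormal at Baseline, the Day 84 count gives the new cases directly. Otherwise the per-visit counts only bound the number.

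**The case against.** The strongest reply is that the information is not lost. A reader might infer from the missing table that new abnormalities on treatment are invisible. The documents do not support that. Listing 16.2.8.2.1.3 puts each subject's Baseline and Day 84 results side by side under a treatment-group heading. Protocol 8.1.1 also counts an abnormal laboratory finding as a possible adverse event, so some new abnormalities may reach the TEAE tables. Both facts stand. However, the protocol promises the listing in addition to shift tables and an abnormal-value summary, and comparing arms from it means a hand tally over up to 360 subjects. The adverse event route catches only what an investigator records as an event.

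A second reply concerns SAP 6.10.3. Its shift rule is tied to normal ranges, and the shell applies it as below, within or above limits. A result without numeric limits does not fit that scheme, so the numeric-only table can be defended as a fair reading of 6.10.3. It is therefore not safe to say that the shells contradict the SAP's own text. The mismatch with protocol 9.4.2 remains, because that sentence has no such qualifier. Protocol 9.1 leaves the structure of tables to the SAP, but that does not amount to dropping a stated analysis without saying so.

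Third, the result types are unknown. A reader might take it as settled that five of the seven items lack a shift table. The documents support only a range, and the upper end rests on how the laboratory reports three of the items.

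Finally, no efficacy estimate, test or analysis population is touched, and the documents name no urinary or renal safety concern. That is right, and it is why this is a small point.

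**Conclusion.** The point holds as a minor reporting gap. For character-valued urinalysis items, the SAP provides neither the shift table nor the abnormal-value summary to which protocol 9.4.2 commits, and section 8 declares no departure. New abnormalities in these items generally cannot be counted by arm from any planned laboratory summary table, although they can be found subject by subject in the listing.

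The gap covers between two and five of the seven routine items. Five requires protein, glucose and leukocyte esterase to be reported in grades. In the illustration, equal counts of 6 leave the number of new positives anywhere from 0 to 6. The upper end, 7.9%, is a share of the 76 paired subjects and should not be read as a share of the 90-subject arm, where 6/90 = 6.7%. The counts and the missing-sample rate are assumptions. Only the structural conclusion, that per-visit counts bound but usually do not fix the number, is independent of them.

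**What to change.** Add one Baseline by Day 84 shift table for character urinalysis, by arm, in the safety population among subjects with both results. Classify each result as normal or abnormal by the laboratory's reference indicator, for which the listing layout already has a column. Limit the table to items that have such an indicator, and keep Table 14.3.1.2.3.3 as a supplement for the full category detail. State in the SAP which urinalysis items are treated as numeric and which as character. If the sponsor prefers not to add the table, section 8 should record the omission and the reason.

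The cost is one more safety table, built from data already collected. Trial conduct, sample size and the efficacy analyses are unaffected.
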